## Sample collection plan

Study visit (day/week)	Screening & Vist (Day)	Treatment & Follow &Up (Week)	Treatment & Follow &Up (Week)	Treatment & Follow &Up (Week)
	-21 to 0	1	8	12
Window period (day)	0	0		
Informed consent	x			
Inclusion and exclusion criteria	x			
Demographics and medical history	x			
Pregnancy test (if applicable)	x	x		
Infusion of FMT		Xxx (The Bacterial solution was given at an interval of one day, and a total of 100 mL was transplanted 3 times)		
Mayo score (including MES)	x		x	
Clinical laboratory test	x	x	x	
Fecal calprotectin	x	x	x	x
Adverse.events/serious adverse events		x	x	x

Follow-up Time Points

Groups  (40 Patients/Group)	Samples	Before FMT ( Day )	Follow Up ( Week )	Follow Up ( Week )	Follow Up ( Week )
		Baseline (0)	1	8	12
Fresh fecal bacterial solution  (Normal /Ethnic Han Donor)	Stool	✓	✓	✓	✓
	Biopsies	✓			✓
	Food Record Questionnaire	✓	✓	✓	✓
Fresh fecal bacterial solution  ( Bai Ethnic Donor)	Stool	✓	✓	✓	✓
	Biopsies	✓			✓
	Food Record Questionnaire	✓	✓	✓	✓

Note: (The procedures of sample collections and subpackaging are as follows)

- ① Study stool: The stool of patients are collected and packed into 2ml cryogenic vials.
- ② Study biopsies: One piece was selected from the ileocecal region and two pieces were taken from the most severe lesion of the rectum (10cm from the anus) and placed in a 2ml cryopreserved tube.

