## **5. Study Process:**

## Groups

Groups	Fresh fecal bacterial solution (Ethnic Han Donor)	Fresh fecal bacterial solution (Bai Ethnic Donor)
Planned enrollment	50 Patients	50 Patients
Planned completed 12-week follow-up	30 Patients	30 Patients

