## **5. Assessment Schedule (Table 2)**

### **1. Screening and Group Assignment Visit (-21 Days to Day 0)**

For all consenting patients, baseline demographic and clinical information was collected prior to group assignment, including: Age, gender, and smoking status (current smoker, former smoker, or non-smoker).

- (1) Use of nonsteroidal anti-inflammatory drugs (NSAIDs) or other anticoagulants.
- (2) Use of proton pump inhibitors (PPIs), H2 receptor blockers (H2RB), or other antacids.
- (3) Presence of primary sclerosing cholangitis (PSC).
- (4) History of appendectomy.
- (5) Duration and severity of ulcerative colitis (UC).
- (6) Current treatments and medications.
- (7) Self-reported medication adherence.

Eligible participants were then randomly allocated in a 1:1 ratio to two parallel groups to receive FMT from either a Han donor or a Bai donor.

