#### 10. Sample Size

The study includes 50 UC recipients for FMT from Bai donors and 50 UC recipients for FMT from Han donors, totaling 100 participants.

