#### 11. Statistical Analysis

Continuous variables will be expressed as means (SD) and compared between groups using unpaired t-tests. Categorical variables will be compared using the chi-square test or Fisher's exact test. A modified intent-to-treat analysis will include all participants who have received at least one FMT treatment. Participants requiring additional treatment, violating the study protocol, failing to discontinue corticosteroids by week 12, or discontinuing the study for any reason will be considered treatment failures. Per-protocol analysis will include participants who completed the 12-week blind treatment course without protocol violations. Missing data were handled using complete-case analysis in the primary analysis. A two-sided p-value of <0.05 will be considered statistically significant. Safety data will be summarized using descriptive statistics. All statistical analyses will be performed using R (4.0.5).

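### The per-group number is 50 in two places but 40 in the sampling table, and two conflicting dropout rules leave the primary-analysis number at about 30 or about 50

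*Combined protocol and SAP*

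**What the plan says.** Three per-group numbers appear in the current text.

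- **50.** Section 10 reads "The study includes 50 UC recipients for FMT from Bai donors and 50 UC recipients for FMT from Han donors, totaling 100 participants". The Groups table in section 5 agrees: its row "Planned enrollment" shows 50 for each donor group.
- **40.** In the sample collection plan, the Follow-up Time Points table (stool, biopsies and food records, from baseline to week 12) is headed "40 Patients/Group".
- **30.** The Groups table row "Planned completed 12-week follow-up" shows 30 for each donor group.

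Section 11 determines how many participants enter the analysis, and it does so twice. First, "A modified intent-to-treat analysis will include all participants who have received at least one FMT treatment", and participants who leave the study, whatever the reason, are counted as treatment failures. A few lines later, "Missing data were handled using complete-case analysis in the primary analysis". The section does not say which rule applies to a treated participant who leaves before week 12.

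Neither section 10 nor section 11 states a power, an expected success rate, a target difference or a dropout rate.

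**The concern.** There are two separate problems.

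The first is the header. A sampling table that starts at baseline should carry the enrolled number unless it describes a subset, and nothing says that it does. The section on treatment and follow-up describes stool collection and the two colonoscopies with biopsies for participants in general. Whether 80 or 100 people supply specimens bears on the microbiota outcomes, which are secondary outcomes 4 to 8.

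The second is the denominator of the primary comparison. With a planned 40% loss, keeping dropouts as failures or leaving them out changes the analysed number by up to 20 per group. It also changes the success proportion. Section 10 cannot state a meaningful precision until section 11 settles this, and an undecided rule leaves a choice that could be made after the data are seen.

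**Working it through.** **Inputs from the documents:** 50 enrolled and 30 completers per group (section 5, Groups table); 50 per group and 100 in total (section 10); 40 per group (Follow-up Time Points table); allocation 1:1 (screening and group assignment visit); two-sided 5% level (section 11).

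**Assumed, because the documents give no values:** success rates of 20%, 30% and 40% in the reference group, and 80% power.

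**Step 1. Do the headcounts fit together?** The 50 per group cannot be reproduced from a power calculation, because none is given. As enrolment and completers, 50 and 30 are consistent:

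- implied loss = 1 − 30/50 = 40%, and 30/(1 − 0.40) = 50.

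The 40 fits neither row without a rate that the documents do not state:

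- 50 to 40 needs a loss of 1 − 40/50 = 20%;
- 40 to 30 needs a loss of 1 − 30/40 = 25%.

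**Step 2. How many enter the primary comparison?**

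| Rule in section 11 | Treated dropout is | Per group | Total |
|---|---|---|---|
| Discontinuation is failure, modified intent-to-treat | kept, counted as failure | up to 50 | up to 100 |
| Complete-case | left out if the outcome is missing | possibly about 30 | about 60 |

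The first row says up to 50 because a randomised participant who never receives FMT is outside that population. The 40 matches neither row.

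**Step 3. What does the difference in number mean?** With d = p2 − p1 and p̄ = (p1 + p2)/2,

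power = Φ{ [d − 1.96·√(2p̄(1 − p̄)/n)] / √([p1(1 − p1) + p2(1 − p2)]/n) }.

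Check at p1 = 0.30:

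- n = 50, d = 0.275: (0.275 − 1.96 × 0.0992)/0.0953 = 0.845, power 80%.
- n = 30, d = 0.354: (0.354 − 1.96 × 0.1290)/0.1206 = 0.840, power 80%.

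The last two columns give the 95% CI half-width for the risk difference when both groups share the assumed rate, 1.96·√(2p(1 − p)/n). At p = 0.30 and n = 50 this is 1.96·√(0.42/50) = 0.180. All entries are in percentage points.

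| Assumed rate | Detectable, n = 50 | Detectable, n = 30 | Half-width, n = 50 | Half-width, n = 30 |
|---|---|---|---|---|
| 20% | 26.0 | 34.3 | 15.7 | 20.2 |
| 30% | 27.5 | 35.4 | 18.0 | 23.2 |
| 40% | 27.6 | 35.1 | 19.2 | 24.8 |

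**Step 4. The rule changes the rate as well as n.** If 20 of 50 are lost and all count as failures, the success proportion cannot exceed 30/50 = 60%. A true 40% plus 27.6 points would be 67.6%, which is out of reach under that loss. The n = 50 columns therefore show the effect of number alone. They do not show that the failure rule is the more sensitive analysis.

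**Step 5. Can the choice change a conclusion?** Take assumed counts of 18 and 9 successes, all among completers:

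- complete-case: 18/30 = 60% against 9/30 = 30%, Fisher's exact p = 0.037;
- failure rule: 18/50 = 36% against 9/50 = 18%, Fisher's exact p = 0.070.

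The same successes fall on opposite sides of the 5% level. These counts are an illustration and not a forecast.

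**The case against.** The strongest reply is that only one figure is actually out of line. The 50 and the 30 stand in one table under labels for two different quantities, so the planned loss is disclosed. That is right, and those two numbers do not contradict each other.

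A reader might go further and infer that the plan as written delivers only about 30 per group, so that the sample size in section 10 is not the one the primary analysis will use. The documents do not support that. It takes the complete-case sentence alone and ignores the failure rule and the modified intent-to-treat population in the same section, which together keep the number near 50. Even under complete-case handling, completers need not equal complete cases. The follow-up colonoscopy may take place at 8 to 12 weeks, so someone assessed then and lost before week 12 may or may not count as missing. About 30 is one possible reading.

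A reader might also infer that a stated power or precision is wrong. None is stated, and the trial calls itself a pilot, so nothing of that kind is contradicted. Pilot status does not remove the need for one enrolment target and one dropout rule, however, and section 11 does plan a significance test: "A two-sided p-value of <0.05 will be considered statistically significant".

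Finally, the 40 may simply be a leftover header. That is possible, and since the two places that set enrolment agree on 50, the header is unlikely to govern recruitment. It still has to be reconciled, because nothing tells the reader whether 80 or 100 people are to be sampled.

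**Conclusion.** The point holds in two parts.

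The 40 per group in the sampling table contradicts the 50 in sections 5 and 10, and nothing in the documents explains it.

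Separately, the number behind the primary comparison is undetermined. It is about 50 per group if discontinuation counts as failure, and possibly about 30 if the complete-case sentence governs. At assumed success rates of 20% to 40%, that is the gap between a detectable difference of about 26 to 28 points and one of 34 to 35 points at 80% power. These sizes rest on the assumed rates, a normal approximation, and a loss that matches the planned 40%. The existence of the two conflicts does not depend on any of these assumptions. Both should be resolved before the analysis.

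**What to change.** 1. **Sample collection plan.** Change the Follow-up Time Points header to match the enrolment target. If 40 is a subset, label it so and give its selection rule.
2. **Section 11.** State one rule for participants without a week-12 outcome in the primary analysis, and say whether an assessment in the 8-to-12-week window counts as that outcome. If the other rule is kept, name it as a sensitivity analysis.
3. **Section 10.** Give the enrolled number, the expected loss and its basis, and the number entering the primary analysis under the chosen rule. Add the confidence-interval half-width for that number over a range of assumed success rates, as counted under the same rule.

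Step 3 depends on step 2. The cost is one table header and a few sentences in sections 10 and 11. The change proposes no added enrolment. The downside is that the stated number and its precision may look less favourable than 50 per group does now.

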## **7. Randomization, Blinding, and Treatment Protocols:**

### **1. Randomization:**

Randomization codes will be computer-generated. Subjects will be randomized according to the sequence of these codes.

### **2. Blinding Maintenance:**

This trial adopts a single-blind design, where participants will be blinded to the identity of the FMT donor, while investigators will be aware of the donor identity. The donor's identity will only be accessible to a limited number of staff responsible for preparing the FMT solutions.

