## 4. Methods:

**1. Study Design:** This is a patient single-blind, single-center, randomized, parallel-group pilot clinical trial without placebo control. Patients will be randomized to either the Han donor or the Bai donor and followed up for a 12-week period. Subjects will undergo follow-up assessments for up to 12 weeks in accordance with the same schedule as the blinded phase (i.e., FMT administration at baseline, weekly telephone follow-up at week 1, 8, and on-site follow-up visits at week 12). Subjects who are randomized to the FMT arm or who do not wish to enter the open-label phase will be deemed to have completed the study, and no further follow-up will be arranged.

Note: Single-center means all experimental activities are conducted at the same location.

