### **2. Treatment and Follow-Up (Week 0 to Week 12)**

Participants will undergo two colonoscopies with biopsies performed at two time points: before treatment, at 8 – 12 weeks post-FMT

Stool samples will be collected at the following times: before treatment, at the end of FMT treatment, 8 weeks post-FMT, 12 weeks post-FMT.

During each visit, Mayo scores (including endoscopic subscoring) were evaluated by blinded outcome assessors. Biopsies were performed for histological assessments, and histological scoring was conducted by a blind pathologist. A dedicated telephone line was available for patients to report any adverse events or worsening of symptoms between scheduled visits. All investigators were aware of group allocation, while endoscopists, pathologists, and outcome assessors remained fully blinded to group assignments to minimize assessment bias.

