### **3. Treatment Protocol in Emergency Situations:**

In cases of medical emergencies requiring unblinding for patient care, investigators will be allowed access to the donor allocation. Donor allocation should remain blinded unless necessary to ensure the participant's urgent medical care. The rationale for unblinding, along with the date and details of the unblinding, must be clearly documented. All participants will undergo follow-up by week 6 unless they explicitly decline.

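### The protocol gives incompatible rules on whether investigators know the donor, and no blinded person is named for the non-score failure calls that feed the primary result

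*Combined protocol and SAP*

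**What the plan says.** All references are to the combined protocol and SAP.

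- **Section 4, Study Design:** "This is a patient single-blind, single-center, randomized, parallel-group pilot clinical trial without placebo control".
- **Section 7.2, Blinding Maintenance, first sentence:** "participants will be blinded to the identity of the FMT donor, while investigators will be aware of the donor identity".
- **Section 7.2, second sentence:** "The donor's identity will only be accessible to a limited number of staff responsible for preparing the FMT solutions".
- **Assessment Schedule, Treatment and Follow-Up:** "All investigators were aware of group allocation, while endoscopists, pathologists, and outcome assessors remained fully blinded to group assignments". The same paragraph has the Mayo score, including its endoscopic component, rated by blinded assessors, and histology read by a blinded pathologist.
- **Section 7.3, Emergency Situations:** investigators may obtain the allocation in a medical emergency, with reason and date documented. Otherwise, "Donor allocation should remain blinded unless necessary to ensure the participant's urgent medical care".
- **Section 7.1, Randomization:** codes are computer-generated and "Subjects will be randomized according to the sequence of these codes". No code holder and no concealment method are given.
- **Section 11, Statistical Analysis:** treatment failures include "Participants requiring additional treatment, violating the study protocol", as well as patients still on corticosteroids at week 12 and those who discontinue for any reason. Per-protocol membership requires freedom from protocol violations. The section does not say who makes these determinations, or whether that person is blind to donor.

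**The concern.** A site needs one answer to the question of whether the investigator knows the donor, and the protocol gives two. If investigators know, the restriction in the second sentence of section 7.2 is breached and the emergency route in section 7.3 has no purpose. If they do not know, the first sentence of section 7.2 and the Assessment Schedule are wrong.

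The answer matters because section 11 can turn a patient into a failure on grounds other than the Mayo score. Whether a patient needed additional treatment or violated the protocol can involve judgement, and neither term is defined. The section on prohibited medications leaves more room: it keeps users of such drugs in the study with outcomes still assessed, but does not say which recorded use counts as a violation under section 11.

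The Background also expects that microbiota from minority-region populations may improve FMT efficacy. That is not evidence of bias, but it is the setting in which discretionary calls should be made without knowledge of the arm.

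**Working it through.** **Step 1. Compare the rules.**

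| Place | Do investigators know the donor? |
|---|---|
| Section 7.2, first sentence | Yes |
| Assessment Schedule, Treatment and Follow-Up | Yes, all of them |
| Section 7.2, second sentence | No; preparation staff only |
| Section 7.3 | No, except in an emergency |

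Reading investigators in section 7.2 as meaning only the preparation staff does not rescue the text, because the Assessment Schedule says all investigators. The patient single-blind label in section 4 does not settle it either, because the last two rows contradict that label.

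**Step 2. Trace what unblinded knowledge can reach.**

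- Mayo components and histology: protected, scored blind.
- Additional treatment, violation, steroid non-discontinuation and discontinuation: these set failure under section 11, with no blinded decision-maker named.
- Per-protocol membership: depends on the violation call, so the same gap applies.
- Eligibility: settled before allocation (Assessment Schedule, Screening and Group Assignment) and not part of the failure rule. The investigator-judged entry items (remission at entry, individual review of minor surgery) are exposed only if upcoming codes can be foreseen. That is the concealment gap in section 7.1, a separate matter from section 7.2.

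**Step 3. Illustrate the size.** Section 10 gives 50 per arm with no response rate, effect size or power, so there is no plan figure to reproduce.

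Inputs from the documents: n = 50 per arm (section 10); two-sided 0.05; chi-square or Fisher's exact test (section 11).

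Assumptions not in the documents: the same true success rate p in both arms (30%, range 20% to 50%); a share f of the successes in one arm only is miscalled as failure (10% to 30%).

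The false-positive rate is the sum, over all pairs (a, b) with test p-value below 0.05, of Bin(a; n, p) × Bin(b; n, p(1 − f)). The chi-square test has no continuity correction. The spurious difference is p × f, and the expected number of patients miscalled is n × p × f.

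At n = 50 and p = 0.30:

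| f | Spurious difference | Patients miscalled | Chi-square | Fisher |
|---|---|---|---|---|
| 0 | 0 points | 0 | 0.050 | 0.031 |
| 10% | 0.30 × 0.10 = 3 points | 50 × 0.03 = 1.5 | 0.063 | 0.040 |
| 20% | 0.30 × 0.20 = 6 points | 50 × 0.06 = 3 | 0.104 | 0.070 |
| 30% | 0.30 × 0.30 = 9 points | 50 × 0.09 = 4.5 | 0.179 | 0.128 |

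**Sensitivity to the assumed rate.** At f = 20% with p from 20% to 50%, the chi-square rate is 0.086 to 0.184 and the Fisher rate 0.048 to 0.134. With f = 0 over the same range they are 0.050 to 0.057 and 0.028 to 0.035.

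**Sensitivity to the denominator.** The Groups table plans for 30 completers per arm, and section 11 both counts discontinuation as failure and calls the primary analysis complete-case, so the effective n is unclear. At 30 per arm and p = 30%, f = 20% gives 0.080 (chi-square) or 0.047 (Fisher).

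**The case against.** Single-blind with blinded assessors is a declared and legitimate design. The primary outcome is a Mayo composite scored blind, and participants are blind too, so withdrawals they initiate are made without knowledge of the donor. No section says investigators make the additional-treatment or violation calls. The wording conflict could be cured by editing alone, in either direction.

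Most of this stands, and it narrows the point to the non-score triggers and per-protocol membership. That investigators make those calls is an inference; the text supports only that no blinded person is assigned. Editing toward full investigator awareness would remove the contradiction but leave that gap open.

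A reader might infer more than the documents support:

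- **That investigator awareness biases eligibility, and eligibility calls set primary failures.** Eligibility precedes allocation and is absent from the failure rule. Nor do the documents say investigators can foresee codes: no blocks and no investigator access to the list are described. What can be said is that concealment is not stated.
- **That five miscalls, moving one arm by 5/50 = 10 points, give the size of the problem.** At an assumed 30% rate, one arm expects 0.30 × 50 = 15 successes, so five is a third of them, all miscalled in one direction. That lies beyond the top of the range above.
- **That the bias can be removed at no cost.** Coded labels and code custody are additional steps, and the documents do not say that preparation staff are separate from investigators.

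**Conclusion.** The contradiction between the Assessment Schedule and the first sentence of section 7.2, on one side, and the second sentence of section 7.2 and section 7.3, on the other, is certain from the text. It touches the primary result through one route: section 11 lets non-score events set failure and does not say that anyone blind to donor decides them. The missing concealment statement in section 7.1 is a related but separate gap.

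The size is conditional. With assumed miscalling of 10% to 30% of one arm's successes at an assumed 30% rate and 50 per arm, the chi-square false-positive rate moves from 0.050 to 0.063–0.179 and Fisher's from 0.031 to 0.040–0.128. At the low end Fisher's test stays below 0.05, although the estimated difference is still shifted. Nothing in the documents shows that such miscalling would occur, in which direction, or how often. The point should be corrected, but it does not undermine the blinded Mayo assessment.

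**What to change.** 1. In section 7.2, delete the clause giving investigators the donor identity. In the Assessment Schedule, delete the statement that all investigators knew the allocation. Section 7.3 then works as written and stays.
2. State in section 7.1 that only the preparation staff already named in section 7.2 hold the code list, and that they release a coded suspension after eligibility is signed off. This also supplies the missing concealment statement.
3. In section 4, describe the trial as participant-, investigator- and assessor-blind.
4. In section 11, assign the failure and violation calls, and so per-protocol membership, to staff blind to donor, working from definitions that the sponsor writes in advance. If some investigators must know the donor, this step still protects the primary result.

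The cost is a small burden of coded labels and code custody. Both arms receive fresh suspension by the same route, endoscopists are already blinded, and an emergency route is already written. Sample size, alpha and study procedures do not change.
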